The Effect of Blood Flow Restriction Therapy Following Anterior Cruciate Ligament Reconstruction

[name]

Inova Medical Group – Sports Medicine
[name]
10/13/2020

Table of Contents

SECTION	PAGE
1. INTRODUCTION	1
2. STUDY DESIGN AND SUBJECT SELECTION	3
3. STUDY METHODS AND PROCEDURES	4
4. STATISTICAL CONSIDERATIONS AND DATA ANALYSIS	8
5. HUMAN SUBJECTS PROTECTION	9
6. SUBJECT COMPENSATION	9
7. ADVERSE EVENT REPORTING	10
8. FUNDING	10
9. CONFLICTS OF INTEREST	10
10. FACILITIES AND EQUIPMENT	10
11. OUTSIDE CONSULTANTS/COLLABORATORS	10
12. CONTRACTUAL AGREEMENTS	10
13. REFERENCES	11

ABSTRACT

Title: The Effect of Blood Flow Restriction Therapy on Outcomes Following Anterior Cruciate Ligament Reconstruction

Short Title: Effect of BFR on ACL Reconstruction

Rationale: To investigate the effect of Blood Flow Restriction (BFR) exercises on the recovery process following an Anterior Cruciate Ligament (ACL) reconstruction.

Objectives: The main objective is to determine the impact of BFR therapy, in comparison to a standard rehabilitation protocol, on the functional outcomes of patients recovering from ACL reconstruction. The secondary objective is to determine if there are any adverse effects associated with BFR exercises.

Study Type: Prospective Randomized Control Trial (Level 1)

Study Design: Prospective Randomized Control Trial

Study Methodology:

Prospective data will be collected on 150 patients total, randomly divided into two groups based on the physical therapy regimen: (1) standard ACL rehabilitation (control group), and (2) standard ACL rehabilitation plus BFR therapy (BFR group). Patients in the BFR group will begin BFR therapy post-operative week 2, which will consist of the standard ACL rehabilitation exercises augmented with a pressure cuff during the session.

Inclusion criteria will consist of patients 13-55 years undergoing ACL reconstruction. Exclusion criteria include concomitant ligament reconstruction or concurrent procedures that require delayed weight bearing such as High Tibial Osteotomy (HTO), microfracture, etc. Additional exclusion criteria include history of DVT/PE, immunocompromising conditions, history of coagulation disorders or current use of anticoagulants, and pregnancy.

Outcome measures will include Knee Injury and Osteoarthritis Outcome Score (KOOS), International Knee Documentation Committee Subjective Knee Evaluation Form (IKDC), Limb Symmetry Index (LSI), thigh circumference, and return to sport. Baseline scores will be obtained prior to surgery when applicable. Outcomes will be measured at designated time intervals for 2 year following surgery.

Statistical Methodology: Data will be reviewed by a trained statistician. Repeated-measures analysis of variance (ANOVA) will be used to evaluate all patient-reported outcome surveys at multiple time points. All statistical tests will use two-tailed hypothesis testing with the statistical significance a priori set at alpha, α , is equal to 0.05

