1. INTRODUCTION

1.1 Specific Aims

It is hypothesized that blood flow restriction (BFR) therapy can help stimulate muscular development while recovering from surgery, producing a more rapid increase in function and an expedited return to playing sports.

Our primary objective is to determine the effect BFR exercises on the functional outcomes of patients recovering from ACL reconstruction, compared to that of a control group using a standard rehabilitation protocol. The secondary objective is to determine if any adverse effects or complications are associated with BFR therapy.

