1.2 Hypotheses

It is hypothesized that patients undergoing BFR will show significantly improved outcome measurements throughout rehabilitation after ACL reconstruction.

	Rehabilitation with BFR	Standard Rehabilitation without BFR
KOOS	Better	Worse
IKDC	Better	Worse
VAS	Better	Worse
Limb Symmetry Index (LSI)	Better	Worse
Thigh circumference	Better	Worse
Return to sport	Better	Worse

Null Hypothesis: There is no statistically significant difference in the functional outcomes of patients using a standard ACL rehabilitation protocol versus a standard ACL rehabilitation protocol augmented with BFR therapy.

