3.4.2 Secondary Outcomes

The secondary objective is to determine if BFR exercises are associated with adverse effects such as numbness, tourniquet-site pain, and bruising.

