 - International Knee Documentation Committee Subjective Knee Evaluation Form (IKDC)
 - VAS
 - Completed at 3 month intervals
 - Baseline (prior to surgery)
 - 3 months, 6 months, 9 months, 12 months, 24 months
- Limb Symmetry Index (LSI)
 - Consists of 4 assessments:
 - Single hop for distance, triple hop for distance, cross-over hop for distance, 6 meter hop for time
 - Compare operative leg vs. non-operative leg
 - Completed at 3 month intervals after surgery
 - 3 months, 6 months, 9 months, 12 months
- Quadriceps muscle assessment
 - Thigh circumference
 - Compare operative leg vs. non-operative leg
 - Completed at 3 month intervals
 - Baseline (prior to surgery)
 - Just for thigh circumference
 - 3 months, 6 months, 9 months, 12 months
- Return to sport
 - Defined as the date that patient is cleared for return to all sports without restriction by their physician utilizing an objective return to play criteria.

Adverse Effects:

- Therapist-completed survey of BFR:
 - Administered during PT session
 - Assesses for bruising, tourniquet-site pain, numbness, compartment syndrome, rhabdomyolysis
- Miscellaneous complications:
 - Ie: DVT/PE, reinjury, return to operating room, etc.
 - Will be recorded during office visits

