4. STATISTICAL CONSIDERATIONS/DATA ANALYSIS

4.1 Sample Size

We are currently aware of no studies that use KOOS, IKCD scores, limb symmetry index, or return to play for BFR therapy after ACL reconstruction. However, studies [10, 11, 12, 13] of similar populations have found OOS, IKDC, LSI, RTP values of 91.5, 87.5, 79%, and 209 days, respectively. Using those estimates, a power analysis was done and sample size of 150 provides enough power (80%, with an alpha of 0.05) to detect clinically significant changes in these values, while simultaneously accounting for any potential loss-to-follow-up or early withdrawal from the study.

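### For the surveys, a baseline-adjusted mixed model has at least as much power as repeated-measures ANOVA for the same contrast, and stays valid under missing-at-random dropout

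*Combined protocol and SAP*

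**What the plan says.** The abstract, under Statistical Methodology, states: "Repeated-measures analysis of variance (ANOVA) will be used to evaluate all patient-reported outcome surveys at multiple time points". Tests are two-sided at 0.05. Section 4.2 adds descriptive summaries and unspecified measures of association, so no other comparison of the arms on the surveys is named. KOOS and IKDC are among the primary outcomes (3.4.1).

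Section 3.6 schedules KOOS, IKDC and VAS before surgery and at "3 months, 6 months, 9 months, 12 months, 24 months". The abstract confirms the first of these: "Baseline scores will be obtained prior to surgery when applicable".

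Three things are not stated: how the pre-surgery score enters the analysis, how a patient with a missed survey is handled, and whether the arm effect or the arm-by-time effect decides. The stated aims point to different tests. Section 1.1 speaks of "producing a more rapid increase in function and an expedited return to playing sports", whereas section 1.2 expects that "patients undergoing BFR will show significantly improved outcome measurements throughout rehabilitation after ACL reconstruction".

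Section 4.1 presents 150 patients as sufficient "while simultaneously accounting for any potential loss-to-follow-up or early withdrawal from the study", without giving a loss rate.

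**The concern.** Repeated-measures ANOVA in its usual form needs a complete set of visits from each patient, so one missed survey out of several removes all of that patient's data. It also makes no use of the baseline score to reduce between-patient variance unless baseline is added as a covariate. A mixed model uses both the baseline and the incomplete patients, on data the trial already plans to collect.

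Three things are at stake:

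- **Power.** It may be lost on two of the primary outcomes.
- **Bias.** Comparing only the patients who remain can bias the arm comparison if dropout depends on earlier scores differently in the two arms. Only one arm wears the cuff, for which 3.4.2 anticipates "adverse effects such as numbness, tourniquet-site pain, and bruising", so such a difference is conceivable.
- **Choice of effect.** If the deciding effect is left open, it can be chosen after results are known.

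**Working it through.** **The plan's own figure.** The 150 in 4.1 cannot be reproduced, because no difference, SD or loss rate is given. Solving backwards at 80% power and two-sided 0.05, the detectable difference is 2.80 × √(2/n) SD. That is 0.457 SD with n = 75 per arm, and 0.511 SD with 20% loss (n = 60).

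**Inputs.** From the documents: 75 per arm (2.4), five post-operative surveys plus baseline (3.6), two-sided 0.05 (abstract). Assumed: a constant 0.40 SD effect, correlation 0.5 between post-operative visits, baseline correlation r from 0.1 to 0.5, and 0%, 5% or 10% of surveys missed independently at each visit.

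**Post-operative ANOVA, arm effect, nothing missed.** The variance of a patient's five-visit mean is (1 + 4 × 0.5)/5 = 0.60. The standard error of the difference is √(2 × 0.60/75) = 0.126, so the effect is 0.40/0.126 = 3.16 standard errors. Power is 88%.

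**Adding baseline, nothing missed.** The variance becomes 0.60 − r². For r = 0.1, 0.2, 0.3 and 0.5 this is 0.59, 0.56, 0.51 and 0.35, a fall of 1.7%, 6.7%, 15% and 42%.

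**Missed surveys.** An ANOVA on patients complete at the five post-operative visits keeps 150 × 0.95⁵ = 116 patients, or 150 × 0.90⁵ = 89. The mixed model keeps every available survey; its power comes from the expected information over all missing-data patterns.

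| Missed per visit | Complete-patient post-operative ANOVA | Mixed model, no baseline | Mixed model with baseline, r = 0.1 to 0.5 |
|---|---|---|---|
| 0% | 88% | 88% | 89–98% |
| 5% | 79% | 88% | 88–98% |
| 10% | 67% | 87% | 88–98% |

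**Where the gain comes from.** With nothing missed, all of it is baseline. With 5% missed, keeping incomplete patients adds about 9 points. Baseline then adds about half a point at r = 0.1, 2 at 0.2, 4 at 0.3 and 10 at 0.5. With 10% missed, keeping incomplete patients adds about 20 points.

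**The contrast matters.** Suppose the effect falls from 0.40 SD at 3 months to 0 at 24 months in equal steps per visit (baseline correlation 0.3, others 0.5, nothing missed). The mixed-model average then has 40% power, ANOVA arm-by-time (baseline as a level, approximate) 61%, and the mixed model's joint test over visits 68%. For a constant effect the order can reverse: with post-operative correlation 0.7 and baseline 0.3, the joint test has 60% and the ANOVA arm effect 80%.

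**Dropout depending on the last observed score, by simulation (2,000 or more trials per setting, about 20% dropout by 24 months).**

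- Opposite directions in the two arms, no true effect: the complete-patient post-operative ANOVA is biased by 0.22 SD with 38% false positives. The mixed model has bias 0.00 and 5.3%.
- One arm only, no true effect, baseline treated as an ANOVA level: the ANOVA is biased by 0.09–0.10 SD with 10–11% false positives. The mixed model has bias 0.00 and 5%.
- Same mechanism in both arms: no bias when there is no effect. With a true 0.40 SD, the complete-patient estimate is 0.36 and the mixed model's is 0.40.
- Dropout depending on the unseen score, opposite by arm, no true effect: both are biased, the ANOVA by 0.22 SD (38% false positives) and the mixed model by 0.07 SD (9%).

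**The case against.** The plan does not say that incomplete patients are deleted or that baseline is a level of time. A comparison against that worst layout measures an assumption and not the plan. This stands. A reader might infer a gain from 63% to 98%, which is what the six-level layout with deletion gives at 5% missed and all correlations 0.5. The fair comparator is the post-operative ANOVA used above.

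A reader might also infer that the gain comes mainly from baseline. The documents give no correlation or missing rate, and a pre-surgery score on an injured knee may predict later scores weakly. The split changes with both figures, so that reading is not supported.

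Nor does the ANOVA ignore the loss allowance in 4.1. Enlarging a trial for loss is exactly an allowance for analysing those who remain. The narrower point is that scattered missed surveys may remove more patients (about 34 of 150 at 5% per visit) than an unstated rate covers.

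Finally, 3.4.2 lists cuff discomforts but does not link them to dropout or to survey scores. The arm-specific dropout scenario is assumed, and withdrawal driven by unseen scores would bias the mixed model too. All of this limits the size of the point. None of it removes the advantage for a fixed contrast.

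**Conclusion.** The point holds as a question of efficiency and specification. ANOVA on complete data is a valid test; the documents do not support calling it wrong, or predicting a biased result.

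For the average post-operative difference, the baseline-adjusted mixed model gains about 0 to 10 points with nothing missed, 9 to 19 with 5% missed per visit and 21 to 31 with 10% missed. These figures assume a constant 0.40 SD effect, post-operative correlation 0.5, baseline correlation 0.1 to 0.5, and complete-patient analysis as the ANOVA's default. The gain is for a like-for-like contrast: an averaged mixed-model contrast can lose to ANOVA arm-by-time if the effect fades. Protection covers missing-at-random dropout only.

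The change should be made, because the data are already planned and the choice is still open in the text. Confidence in the direction is high. Confidence in the size is moderate, because every input beyond sample size, visits and alpha is assumed.

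**What to change.** In the abstract and 4.2, replace the ANOVA for the surveys with a likelihood-based mixed model on all available surveys from all randomised patients. Its terms are arm, visit, arm-by-visit, baseline score and baseline-by-visit, with unstructured covariance. Keep patients with a missing baseline survey through a constrained-baseline form of the model or simple baseline imputation.

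Before data are seen, name one deciding contrast. The average over post-operative visits fits the sustained benefit in 1.2. The joint test over visits, or a single early visit, fits the faster recovery in 1.1.

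State the missing-at-random assumption and add one sensitivity analysis for departures from it, for example a shift applied to missing scores in one arm.

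The cost is revised wording, one decision by the investigators, and modest extra specification and analysis work, which is a real consideration in an unfunded study (section 8). No visits, data or patients are added.

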2.4 Number of Subjects

The goal is to include 150 subjects in the study, which will be divided into 75 patients in the treatment group and 75 patients in the control group.

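### The repeated-measures ANOVA for KOOS, IKDC and VAS names neither the term tested nor a safeguard against non-sphericity; an uncorrected group-by-time test would probably run at about 6% to 9% rather than 5%

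*Combined protocol and SAP*

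**What the plan says.** The only inferential method named for the patient-reported surveys is in the abstract, under Statistical Methodology: "Repeated-measures analysis of variance (ANOVA) will be used to evaluate all patient-reported outcome surveys at multiple time points". The error rate is fixed there too: "All statistical tests will use two-tailed hypothesis testing with the statistical significance a priori set at alpha", at 0.05.

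Section 3.6 lists KOOS, IKDC and VAS as the surveys. They are taken at "Baseline (prior to surgery") and then at "3 months, 6 months, 9 months, 12 months, 24 months". That makes six levels of time if baseline is one of them, and five if it is not. KOOS and IKDC are among the primary outcomes in section 3.4.1.

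Two passages bear on what is to be tested. Section 1.1 expects the intervention to act by "producing a more rapid increase in function and an expedited return to playing sports". Section 1.2 expects that "patients undergoing BFR will show significantly improved outcome measurements throughout rehabilitation after ACL reconstruction".

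Section 4.2 offers descriptive statistics and measures of association. It contains no ANOVA model, no model term, no covariance structure, no sphericity check and no correction, and no other section supplies them.

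**The concern.** In a two-arm repeated-measures ANOVA, a difference between arms in the rate of change is the group-by-time interaction. That is the term that best matches the aim in section 1.1. If baseline is a level of time, the group main effect averages in a score taken before any treatment, which makes the interaction the more natural treatment test.

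The univariate F test of that interaction has its nominal size only under sphericity, meaning that the differences between every pair of visits have the same variance. Visits spread over 24 months, the first on an injured knee before surgery, make this hard to sustain. Correlation that weakens as the gap lengthens breaks it, and so does a spread of scores that changes during recovery.

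At stake is whether a claim that BFR changes the course of recovery on KOOS, IKDC or VAS carries the 5% error rate the abstract promises. A second risk comes from leaving the choice open: corrected and uncorrected p-values can fall on opposite sides of 0.05, and the selection could then be made after the data are seen.

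**Working it through.** **Inputs from the documents.** 75 patients per arm (section 2.4: "75 patients in the treatment group and 75 patients in the control group"); six visits, baseline included (section 3.6); alpha 0.05 (abstract).

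**Inputs assumed.** The documents give no variances or between-visit correlations, so a range of structures was used. All runs had normal errors, complete data and no true effect, with 40,000 simulated trials per structure. The simulation standard error near 5% is √(0.05 × 0.95 / 40,000) ≈ 0.1 percentage points.

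**Test.** The group-by-time F has 6 − 1 = 5 and 5 × (150 − 2) = 740 degrees of freedom. Its 5% critical value is 2.23.

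**Step 1: reproduce the plan's 5%.** With equal variances and equal correlations of 0.5 (sphericity true), the uncorrected test rejected in 4.95% of trials. The stated alpha is recovered, so any excess below comes from the covariance assumption.

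**Step 2: see how sphericity fails.** Take a common SD σ and a correlation r per 3 months that decays with the gap. The variance of a between-visit difference is then 2σ²(1 − r^(gap/3)). With r = 0.8:
- 3-month gap: 2σ²(1 − 0.8) = 0.40σ²
- 12-month gap: 2σ²(1 − 0.8⁴) = 1.18σ²
- 24-month gap: 2σ²(1 − 0.8⁸) = 1.66σ²

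The largest is about 4.2 times the smallest (1.66 / 0.40); sphericity requires them to be equal.

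**Step 3: size of the group-by-time test.** Epsilon is the Greenhouse-Geisser index (1 = spherical; minimum 1/5 with six visits).

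| Assumed structure | Epsilon | Uncorrected F | Greenhouse-Geisser | Multivariate test |
|---|---|---|---|---|
| Equal correlation 0.5, SD 18 falling to 10 | 0.83 | 6.2% | 4.8% | 5.1% |
| Correlation 0.5 per 3 months | 0.82 | 6.3% | 4.9% | 5.0% |
| Baseline correlation 0.2, later visits 0.6 | 0.80 | 6.5% | 5.0% | 5.3% |
| Shared component 0.4 plus serial decay | 0.76 | 6.6% | 4.8% | 5.0% |
| Correlation 0.7 per 3 months | 0.69 | 7.0% | 4.6% | 4.9% |
| Correlation 0.7 per visit | 0.63 | 7.6% | 4.8% | 5.2% |
| Correlation 0.8 per 3 months | 0.62 | 8.0% | 4.9% | 5.0% |
| Correlation 0.9 per 3 months | 0.54 | 8.7% | 4.9% | 4.9% |
| Correlation 0.8 per 3 months, SD 18 falling to 10 | 0.53 | 8.6% | 4.9% | 5.2% |

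**Step 4: check against the usual approximation.** The rejection rate is roughly P(F(5ε, 740ε) > 2.23). This gives 6.2% at ε = 0.83, 8.2% at ε = 0.62 and 9.3% at ε = 0.53, in line with the table. At the floor ε = 1/5 it gives P(F(1, 148) > 2.23) = 13.8%, an extreme bound and not an expectation.

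**Step 5: what changes the result and what does not.**
- At 60 per arm (20% loss, assumed) the last two decay-0.8 structures, without and with falling SD, give 7.9% and 8.6%, so the excess is not a matter of sample size.
- Using only the five post-surgery visits, separate runs of 12,000 trials gave 7.8% uncorrected and 5.0% to 5.2% corrected, so leaving baseline out does not remove it.
- The group main effect, tested on each patient's mean over visits, stays at 5.0%.

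**The case against.** The strongest reply is that the plan never commits itself to the faulty test. No section names a group-by-time term. The hypothesis in section 1.2 is about better results over the whole of rehabilitation, and a group main effect could test that without needing sphericity. Nor does the abstract say the F test will be uncorrected. An epsilon-corrected or multivariate analysis is also repeated-measures ANOVA, and the abstract promises review by a trained statistician, who might well apply one. All of this stands.

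A reader might therefore infer too much in three ways:

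- **That the trial's false-positive rate does exceed 5%.** The documents do not support this. They leave the term and the correction open, and some permissible choices hold 5%.
- **That the visit schedule by itself proves sphericity fails.** It does not. Unequal spacing is not a violation; unequal variances of the between-visit differences are. Violation is likely here, but no covariance data are given.
- **That every outcome is affected.** ANOVA is named only for the patient-reported surveys, not for LSI, thigh circumference, knee extension strength or return to sport.

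It is also fair to say that the wider gap is the lack of any between-group model in section 4.2, and that handling of non-sphericity would be settled once that model is written. That bears on where the sentence belongs. It does not remove the need for one, because the method as named, in its standard form, can miss the stated alpha on the test closest to the aim in section 1.1.

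**Conclusion.** The point holds as a conditional one. The plan does not state which term of the repeated-measures ANOVA is the treatment test or how non-sphericity is handled. If the group-by-time interaction is tested with the uncorrected univariate F, its false-positive rate would probably be about 6% to 9% on each of KOOS, IKDC and VAS, against a stated 5%. If the group main effect is tested, or a corrected or multivariate interaction test is used, the rate is about 5%.

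The size rests on assumed structures: correlations that weaken with time, SDs that change over recovery, or a weakly correlated baseline. The milder structures sit near 6%, so quoting only the upper half of the range would overstate the matter. The inflation is moderate and the remedy nearly free, so this is a cheap improvement and not a threat to the trial.

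**What to change.** In the abstract and in section 4.2, state that the treatment test for KOOS, IKDC and VAS is the group-by-visit contrast, with visit as a categorical factor. Analyse it with a mixed model using an unstructured within-patient covariance and small-sample degrees of freedom. With six visits this needs 6 × 7 / 2 = 21 variances and covariances. The model also keeps patients who miss visits, under the usual missing-at-random assumption, which matters because section 4.1 anticipates loss to follow-up. The mixed model itself was not simulated here; the multivariate test in the table, which likewise leaves the covariance unrestricted, held 4.9% to 5.3%.

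If classical repeated-measures ANOVA is kept, commit to reporting only the Greenhouse-Geisser-corrected interaction test. The two options are alternatives and not equivalents: they use different statistics, differ in power, and the classical ANOVA drops patients with any missing visit.

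The cost is a sentence or two of text. The downside is slightly larger interaction p-values: at ε = 0.62, for example, the corrected test has 5 × 0.62 = 3.1 and 740 × 0.62 ≈ 459 degrees of freedom, and the critical F rises from 2.23 to about 2.60.

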3.4 Endpoints/Outcomes Measurement

3.4.1 Primary Outcomes

The main objective is to determine whether BFR therapy has an effect on the functional outcomes of patients recovering from ACL reconstruction. Functional outcome measures will include Knee Injury and Osteoarthritis Outcome Score (KOOS), International Knee Documentation Committee Subjective Knee Evaluation Form (IKDC), Limb Symmetry Index (LSI), knee extension strength using a dynamometer, and return to sport.

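### Five unranked primary outcomes share a blanket two-sided 0.05 with no success rule, so the plan does not establish control of the trial-level false-positive rate at 5%

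*Combined protocol and SAP*

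**What the plan says.** - **Primary outcomes (3.4.1).** KOOS and IKDC come first, followed by "Limb Symmetry Index (LSI), knee extension strength using a dynamometer, and return to sport". That makes five outcomes, with no order among them and no lead outcome.
- **Significance level (abstract, Statistical Methodology).** "All statistical tests will use two-tailed hypothesis testing with the statistical significance a priori set at alpha", which "is equal to 0.05". The only test named is for the surveys: "Repeated-measures analysis of variance (ANOVA) will be used to evaluate all patient-reported outcome surveys at multiple time points". No contrast is specified.
- **Hypotheses (1.2).** The prediction is of "significantly improved outcome measurements throughout rehabilitation after ACL reconstruction", and a table expects BFR to do better on six measures. A single null covers them together: "Null Hypothesis: There is no statistically significant difference in the functional outcomes of patients" on the two regimens.
- **Sample size (4.1).** 150 patients are said to give 80% power at alpha 0.05, based on reference values for KOOS, IKDC, LSI and return to play. Knee extension strength is absent. No difference, SD or loss rate is given.
- **Analysis (4.2).** Only descriptive statistics and measures of association with predictors are described.
- **Data collection (3.6).** The surveys are taken at baseline and five post-operative visits, and LSI at four visits. LSI "Consists of 4 assessments": "Single hop for distance, triple hop for distance, cross-over hop for distance, 6 meter hop for time". No rule combines them. Return to sport is a clearance date. Knee extension strength is not named.

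**The concern.** The plan does not say what result rejects the null in 1.2. One significant primary, all five, or some pattern across them would each fit the text, and these rules have very different error rates and power.

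Suppose IKDC gives p = 0.03 and the other four are not significant. The protocol cannot then say whether BFR succeeded. The outcome or visit to emphasise could be chosen after the data are seen, and each candidate could be reported as a primary result significant at the pre-set level.

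**Working it through.** **Inputs.** Alpha is 0.05 two-sided for every test (abstract). The number of primary outcomes is k = 5 (3.4.1), or k = 4 if only those in 4.1 count. There are 75 patients per arm (2.4). The documents give no correlation between outcomes, so 0 to 0.9 is assumed, equal for all pairs, with each outcome scored so that a positive value favours BFR.

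**The plan's own figure.** N = 150 cannot be rebuilt without a difference, SD and loss rate. It can be inverted for a single-visit comparison of means with no loss: (1.960 + 0.842) × √(2/75) = 0.457 SD, or 0.460 SD by the t-test. That applies to one test at 0.05.

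**Rule A: any one unadjusted result counts.** BFR is assumed to have no effect on any outcome.

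- Either direction, independent: 1 − 0.95^4 = 18.5%; 1 − 0.95^5 = 22.6%.
- In favour of BFR, independent: 1 − 0.975^4 = 9.6%; 1 − 0.975^5 = 11.9%.
- Correlated cases: equal-correlation multivariate normal, by one-dimensional numerical integration.

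| Assumed correlation | 0 | 0.5 | 0.7 | 0.9 |
|---|---|---|---|---|
| Any false rejection, k = 4 | 18.5% | 15.6% | 13.0% | 9.4% |
| Any false rejection, k = 5 | 22.6% | 18.3% | 14.8% | 10.2% |
| Any falsely favourable result, k = 4 | 9.6% | 7.8% | 6.5% | 4.7% |
| Any falsely favourable result, k = 5 | 11.9% | 9.1% | 7.4% | 5.1% |

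The benchmark for a single test is 5% for the first two rows and 2.5% for the last two.

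**Rule B: all must pass.** The error is at most 5% without adjustment. Power is the cost. If, purely for illustration, each outcome has 80% power, independence gives 0.8^4 = 41% and 0.8^5 = 33%. At correlation 0.5 / 0.7 / 0.9 the figures are 56 / 62 / 70% for four outcomes and 51 / 59 / 69% for five.

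**Comparison.** Under Rule A the 5% fails. Under Rule B the 5% holds, but the 80% does not describe the trial. The plan chooses neither rule.

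**The case against.** Several objections have force.

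- **The plan need not be inflated.** A reader might infer that the trial runs a 22.6% false-positive rate. The documents do not support that, because they never say that one significant outcome suffices. The single null and the all-better table in 1.2 do not favour that rule over an all-must-pass or pattern rule. What stands is that control is not established, not that it is shown to fail.
- **Direction.** A reader might take 22.6% as the chance of falsely declaring that BFR works. It counts rejections in either direction. The favourable-only figures are about half as large. They still exceed 2.5% at every correlation shown.
- **LSI as four tests.** A reader might count the hop tests separately and reach seven or eight tests. No section plans that. The abstract, 1.2 and 3.4.1 list LSI as one outcome, and 4.1 gives it one reference value (79%). What remains is a missing rule for forming that one number.
- **Correlated outcomes.** Positive correlation is likely and reduces the inflation. Even at 0.9, five outcomes give 10.2%, twice the nominal level.
- **Repeated-measures ANOVA.** It could deal with visits for the surveys once a contrast is named. It does not combine outcomes, and the abstract does not extend it to LSI, strength or return to sport.

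**Conclusion.** The concern holds in this form: with five unranked primaries, 0.05 for every test and no decision rule, the plan does not establish a 5% trial-level false-positive rate. The any-one-counts figures depend on that rule being used and on assumed equal correlations of 0 to 0.9. The all-must-pass power figures also assume 80% power for each outcome, which 4.1 does not let a reader verify.

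This must be fixed before outcome data are seen, because a rule written afterwards cannot prevent selection. The seriousness rests on the missing primary and decision rule. The differing outcome lists and the unspecified LSI summary matter here only because they leave the set of tests undefined.

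**What to change.** 1. **Section 3.4.1.** Before outcome data are seen, name one already collected outcome as the sole primary at two-sided 0.05, with one visit or one ANOVA contrast if it is measured repeatedly. The sponsor should choose it to match the hypothesis in 1.2. State that BFR succeeds only if this test is significant in its favour. Make the other efficacy outcomes secondary, either labelled unadjusted and exploratory or tested by Holm only if the primary is significant. The gate is needed: by simulation, a 0.05 primary beside four ungated Holm secondaries gives a family-wise error of 9.7 / 8.3 / 7.1 / 5.5% at correlation 0 / 0.5 / 0.7 / 0.9.

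   *Alternative:* keep several primaries with exactly one test each, apply Holm across them, and define success as at least one Holm-adjusted result in favour of BFR.
2. **LSI.** If it is a primary, state the single summary of its four hop tests.
3. **Section 4.1.** Restate the 80% for the chosen primary, or label it per-outcome and unadjusted.
4. **Outcome lists.** State whether knee extension strength is a primary, and make the abstract, 1.2, 3.4.1, 3.6 and 4.1 agree.

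**Cost.** With one primary, multiplicity requires no extra patients, but the other outcomes lose a stand-alone confirmatory claim. Whether 75 per arm suffices for the chosen primary is unknown, because 4.1 gives no difference, SD or loss rate.

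Under Holm, the first step is 0.05/4 = 0.0125 or 0.05/5 = 0.01. Power for a lone true effect of 0.46 SD at 75 per arm then falls from 80% to about 61% (four) or 58% (five). Restoring 80% would take about 107 or 112 per arm before any loss. If all effects are real and of that size, power for at least one is 74–98% (four) or 73–99% (five) over correlation 0.9 to 0.
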